**Table 3. Belumosudil Dose Decrements**

Belumosudil Dose	Dose Reduction
200 mg BID	200 mg QD
200 mg QD	200 mg QOD

Abbreviations: BID = twice daily; QD = once daily; QOD = once every other day

If the reduced dose is tolerated for 1 complete cycle, then the dose may be escalated to the previous dose.

## 5. STUDY ASSESSMENTS AND PROCEDURES

The Schedule of Assessments is outlined in **Error! Reference source not found.**

CRISS assessments will not be performed on site for the study but rather will be calculated outside of EDC.

### 5.1 SCREENING PERIOD (DAY -29 TO -1)

Informed consent must be obtained before any study-specific samples are taken or study-specific tests or evaluations are conducted. The following assessments at the screening visit are to occur within 29 days of first dose of study drug (Week 1 Day 1 Visit). Study eligibility will be based on satisfying all the study inclusion and exclusion criteria.

At the screening visit, information will be collected, and subjects will have clinical evaluations as follows:

- Informed consent
- Subject demography
- Medical history
- Inclusion/exclusion criteria
- mRSS
- FVC
- Complete PE
- Vital signs
- Weight
- Hematology and chemistry
- 12-lead ECG
- Pregnancy test
- Concomitant medication assessment

### 5.2 TREATMENT PERIOD

After completion of screening procedures, confirmation of subject eligibility and informed consent, the subject will be enrolled into the study and will undergo all subsequent evaluations required by the protocol.

### 5.2.1 Week 1 Day 1 Visit (Baseline)

At the Week 1 Day 1 Visit, subjects will come to the clinic to have the following procedures:

- Confirmation of inclusion/exclusion criteria
- mRSS
- SHAQ-DI
- Physician Global Assessment
- Patient Global Assessment
- PFT\*
- Skin biopsies
- Complete PE
- Vital signs
- Weight
- Hematology and chemistry\*
- Urinalysis\*
- 12-lead ECG
- Pregnancy test
- Dispense study diary
- Study drug administration (belumosudil 200 mg): review with subject
- Dispense study drug
- Concomitant medication assessment
- AE assessment

*\*These assessments do not need to be repeated if they were conducted within 7 days of baseline.*

### 5.2.2 End of Week 2 (Day 15 ± 3) Visit

Subjects will come to the clinic to have the following procedures:

- Symptom-directed PE
- Vital signs
- Weight
- Hematology and chemistry
- Urinalysis
- 12-lead ECG
- Pregnancy test

- Study drug administration
- Concomitant medication assessment
- AE assessment

### 5.2.3 End of Week 4 (Day 29 ± 3 Days) Visit

Subjects will come to the clinic to have the following procedures:

- Symptom-directed PE
- Vital signs
- Weight
- Hematology and chemistry
- Urinalysis
- 12-lead ECG
- Pregnancy test
- Dispense and collect study diary
- Study drug administration
- Dispense and collect study drug
- Concomitant medication assessment
- AE assessment

### 5.2.4 End of Week 8 (Day 57 ± 3 Days) Visit

Subjects will come to the clinic to have the following procedures:

- CRISS
- mRSS
- FVC
- SHAQ-DI
- Physician Global Assessment
- Patient Global Assessment
- Symptom-directed PE
- Vital signs
- Weight
- Hematology and chemistry
- Urinalysis
- 12-lead ECG
- Pregnancy test

- Dispense and collect study diary
- Study drug administration
- Dispense and collect study drug
- Concomitant medication assessment
- AE assessment

### **5.2.5 End of Week 12 (Day 85 ± 3 Days) Visit**

Subjects will come to the clinic to have the following procedures:

- Symptom-directed PE
- Vital signs
- Weight
- Hematology and chemistry
- Urinalysis
- 12-lead ECG
- Pregnancy test
- Collect and dispense study diary
- Study drug administration
- Collect and dispense study drug
- Concomitant medication assessment
- AE assessment

### **5.2.6 End of Week 16 (Day 113 ± 3 Days)**

Subjects will come to the clinic to have the following procedures:

- CRISS
- mRSS
- FVC
- SHAQ-DI
- Physician Global Assessment
- Patient Global Assessment
- Symptom-directed PE
- Vital signs
- Weight
- Hematology and chemistry
- Urinalysis

- 12-lead ECG
- Pregnancy test
- Collect and dispense study diary
- Study drug administration
- Collect and dispense study drug
- Concomitant medication assessment
- AE assessment

### **5.2.7 End of Week 20 (Day 141 ± 3 Days) Visit**

Subjects will come to the clinic to have the following procedures:

- Symptom-directed PE
- Vital signs
- Weight
- Hematology and chemistry
- Urinalysis
- 12-lead ECG
- Pregnancy test
- Collect and dispense study diary
- Study drug administration
- Collect and dispense study drug
- Concomitant medication assessment
- AE assessment

### **5.2.8 End of Week 24 (Day 169 ± 3 Days) Visit**

Subjects will come to the clinic to have the following procedures:

- CRISS
- mRSS
- FVC (if PFT not performed at visit)
- Skin biopsies
- SHAQ-DI
- Physician Global Assessment
- Patient Global Assessment
- PFT (± 7 days)
- Complete PE

- Vital signs
- Weight
- Hematology and chemistry
- Urinalysis
- 12-lead ECG
- Pregnancy test
- Collect and dispense study diary
- Study drug administration
- Collect and dispense study drug
- Concomitant medication assessment
- AE assessment

### **5.2.9 End of Weeks 28 and 32 (Days 197 and 225 ± 3 Days) Visits**

Subjects will come to the clinic to have the following procedures at each visit:

- Symptom-directed PE
- Vital signs
- Weight
- Hematology and chemistry
- Urinalysis
- 12-lead ECG
- Pregnancy test
- Collect and dispense study diary
- Study drug administration
- Collect and dispense study drug
- Concomitant medication assessment
- AE assessment

### **5.2.10 End of Week 36 (Day 253 ± 3 Days) Visit**

Subjects will come to the clinic to have the following procedures:

- CRISS
- mRSS
- FVC
- SHAQ-DI
- Physician Global Assessment

- Patient Global Assessment
- Symptom-directed PE
- Vital signs
- Weight
- Hematology and chemistry
- Urinalysis
- 12-lead ECG
- Pregnancy test
- Collect and dispense study diary
- Study drug administration
- Collect and dispense study drug
- Concomitant medication assessment
- AE assessment

### **5.2.11 End of Week 40, 44, and 48 (Days 281, 309 and 337 ± 3 Day) Visits**

Subjects will come to the clinic to have the following procedures at each visit:

- Symptom-directed PE
- Vital signs
- Weight
- Hematology and chemistry
- Urinalysis
- 12-lead ECG
- Pregnancy test
- Collect and dispense study diary
- Study drug administration
- Collect and dispense study drug
- Concomitant medication assessment
- AE assessment

### **5.2.12 End of Treatment (EOT) Or End of Week 52, (Day 365 ± 3 Days)**

Subjects will come to the clinic to have the following procedures:

- CRISS
- mRSS

- FVC (if PFT not performed at visit)
- SHAQ-DI
- Physician Global Assessment
- Patient Global Assessment
- PFTs ( $\pm$  7 days)
- Skin biopsies
- Complete PE
- Vital signs
- Weight
- Hematology and chemistry
- Urinalysis
- 12-lead ECG
- Pregnancy test
- Collect study diary
- Collection of study drug
- Concomitant medication assessment
- AE assessment

### 5.3 28-DAY FOLLOW-UP VISIT

Subjects will return to the clinic 28 days ( $\pm$  3 days) after their last dose of belumosudil 200 mg. At this visit, the following procedures will be completed:

- CRISS
- mRSS
- SHAQ-DI
- Physician Global Assessment
- Patient Global Assessment
- Complete PE
- PFT
- Vital signs
- Weight
- Hematology and chemistry
- Urinalysis
- 12-lead ECG
- Pregnancy test

- Concomitant medication assessment
- AE assessment

#### **5.4 UNSCHEDULED VISIT**

For subjects requiring an unscheduled visit, the following procedures may be performed at the Investigator's discretion:

- CRISS
- mRSS
- FVC (if PFT not performed at visit)
- SHAQ-DI
- Physician Global Assessment
- Patient Global Assessment
- PFTs
- Complete PE
- Vital signs
- Weight
- Hematology and chemistry
- Urinalysis
- 12-lead ECG
- Pregnancy test
- Collect and/or dispense study diary
- Study drug administration (belumosudil 200 mg)
- Collect and/or dispense study drug
- Concomitant medication assessment
- AE assessment

## 6. EFFICACY AND SAFETY ASSESSMENTS

### 6.1 EFFICACY ENDPOINTS

Efficacy measurements will be performed as outlined in [Appendix A](#).

The primary efficacy endpoint is the effect of belumosudil 200 mg BID on the CRISS at the end of Week 24 in the mITT Population. The CRISS exponential algorithm determines the predicted probability of improvement from baseline, incorporating changes in mRSS, FVC% predicted, SHAQ-DI, and physician and Patient Global Assessments. The outcome is a continuous variable between 0.0 and 1.0 (0-100%). A higher score indicates greater probability of improvement. A CRISS score  $\geq 20\%$  is considered a clinically meaningful improvement. The calculation of CRISS will be performed from data available from the EDC and will not be performed by the investigator (or designee) on site.

Secondary efficacy endpoints include the change from baseline in mRSS, FVC, SHAQ-DI, Physician Global Assessment, and Patient Global Assessment.

Other efficacy outcomes include the change from baseline in mRSS for KD025-treated subjects. The mRSS is a measure of skin thickness rated with scores ranging from 0 (normal) to 3 (severe skin thickening) across 17 different sites. The total score is the sum of the individual skin scores in the 17 body areas (i.e., face, hands, fingers; proximal area of the arms, distal area of the arms, thorax, abdomen; proximal area of the legs, and distal area of the legs, feet), yielding a range of 0 to 51 units. The mRSS has been validated for patients with SSc. A negative change from baseline demonstrates improvement.

The effect of belumosudil will be explored for the change in baseline for SHAQ-DI, which assesses 5 scleroderma-specific Visual Analog Scale (VAS) items to explore the impact of participant's disease. Each VAS item will be rated separately in scale of 0 to 100 mm, with higher scores indicating more severe disease. The 5 items are: (1) intestinal disease, (2) breathing problem, (3) Raynaud syndrome, (4) finger ulcers, and (5) overall disease.

Onset/progression of ILD will be evaluated by the effect of belumosudil in the change in predicted FVC, which is based on institutional standards and will be measured as part of

PFTs, including FEV1, FVC, DLCO, and total lung capacity (TLC). The same equipment and tester should be used during the course of the study to the extent possible. The person responsible for conducting the PFTs will be required to comply with the study guidelines and the American Thoracic Society/European Respiratory Society joint criteria on lung function testing.

### **6.1.1 Primary Efficacy Endpoint**

The primary efficacy endpoint of the study is the efficacy of belumosudil 200 mg BID for CRISS at Week 24.

### **6.1.2 Secondary Efficacy Endpoints**

The secondary efficacy endpoints are:

- Efficacy of belumosudil 200 mg BID CRISS at Weeks 8, 16, 36, and 52
- Efficacy of belumosudil 200 mg BID at Week 24 for:
  - mRSS
  - FVC
  - Physician Global Assessment
  - Patient Global Assessment
  - SHAQ-DI
- Efficacy of belumosudil 200 mg BID at Weeks 8, 16, 36, and 52 compared to baseline for:
  - mRSS
  - FVC
  - Physician Global Assessment
  - Patient Global Assessment
  - SHAQ-DI

### **6.1.3 Exploratory Endpoints**

- [REDACTED]
- [REDACTED]
- [REDACTED]
- [REDACTED]

## 6.2 SAFETY ENDPOINTS

The safety endpoints include (see [Section 9](#) for additional detail on AEs):

- The percentage of subjects with TEAEs and SAEs (CTCAE v5.0)
- Hematological and clinical chemistry parameters
- Urinalysis
- Vital signs: change from baseline in systolic blood pressure, diastolic blood pressure and heart rate
- PEs (complete or symptom-directed)
- 12-lead ECG: mean and maximum change from baseline in QTc(F)
- Pregnancy test

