### 6.2.3 12-Lead ECG

Twelve-lead ECGs will be performed as outlined in the Schedule of Assessments ([Appendix A](#)). ECGs will be recorded after the subject has rested in the supine position for at least 5 minutes.

The following ECG parameters will be collected: PR interval, QRS interval, RR and QTc or QTcF. The ECG findings will be evaluated by a qualified physician for the

presence of abnormalities (qualitative assessment). The physician will assess each ECG as normal, abnormal/not clinically significant, or abnormal/clinically significant.

Abnormalities in the ECG that lead to a change in subject management or result in clinical signs and symptoms are considered clinically significant for the purposes of this study and will be recorded in the AE eCRF. If ECG abnormalities meet criteria defining them as serious, they must be reported as an SAE (**Section Error! Reference source not found.**).

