- H. Women of childbearing potential must have a negative urine pregnancy test. Positive results are to be confirmed with serum testing. In the event of a positive urine test at baseline, serum testing results should be acquired within 48 hours prior to study start.

Note: At Week 1 Day 1 visit, if screening was completed within 7 days of baseline, only the complete PE and vital sign measurements need to be repeated.

Note: CRISS will not be performed on site but rather will be calculated outside of EDC.

[figure not shown]

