3.1.5 Baseline

Baseline value is defined as the valid and last non-missing value obtained within 29 days prior to subject receiving the first study medication, unless otherwise stated under the related assessment section. Baseline can be the day before the first study medication or on the same day as the first study medication if a pre-dose assessment is available. Subjects without data on a parameter before the first study medication will have a missing baseline for this parameter.

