3.9.4 ECG

Descriptive statistics for ECG parameters (i.e., heart rate, PR interval, RR interval, QRS interval, QT interval, and QTcF interval) at each time point with triplicate ECGs will be presented for the values and change from baseline scores (QTcF is the QT interval using Fridericia's correction which is calculated by $QTcF = QT/RR^{1/3}$). In addition the maximum change from baseline will be calculated for each subject and summarized for each scheduled assessment visit.

The number and percentage of subjects with observed QTcF values that satisfy the following conditions will be presented:

- ≤ 450 millisecond (ms)

- >450 to \leq 480 ms
- >480 to \leq 500 ms
- > 500 ms

The number and percentage of subjects having change from baseline QTcF values that satisfy the following conditions will be presented:

- \leq 0 ms
- >0 to \leq 30 ms
- >30 to \leq 60 ms
- > 60 ms

A by patient by visit listing will be generated for ECG results.

REFERENCES

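### The maximum QTcF change is not defined; taken across visits in a single-arm trial it is positive with no drug effect, and a single pre-dose baseline adds avoidable noise

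*Protocol*

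**What the plan says.** **Endpoint.** Protocol 6.2 names "12-lead ECG: mean and maximum change from baseline in QTc(F" among the safety endpoints.

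**Analysis.** SAP 3.9.4 summarises ECG parameters "at each time point with triplicate ECGs will be presented for the values and change from baseline scores", and then says that "the maximum change from baseline will be calculated for each subject and summarized for each scheduled assessment visit". It also plans tables of QTcF level (cut at 450, 480 and 500 ms) and of QTcF change (cut at 0, 30 and 60 ms), and a listing by patient and visit. It does not say whether the change bands classify a subject visit by visit or by the worst visit.

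**Baseline.** SAP 3.1.5 states: "Baseline value is defined as the valid and last non-missing value obtained within 29 days prior to subject receiving the first study medication". SAP 3.9.4 gives no separate rule for ECGs.

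**Schedule.** Protocol 6.2.3 says: "Twelve-lead ECGs will be performed as outlined in the Schedule of Assessments". Appendix A shows an ECG at screening, on Day 1, at Weeks 2, 4, 8, 12, 16, 20, 24, 28, 32, 36, 40, 44, 48 and 52/EOT, and at the follow-up visit, for which Section 5.3 says "Subjects will return to the clinic 28 days" after the last dose. The protocol nowhere mentions triplicate recording. A note to Appendix A says that "if screening was completed within 7 days of baseline, only the complete PE and vital sign measurements need to be repeated", which would waive the Day 1 ECG. Section 5.2.1 does not mark the ECG among the assessments that may be skipped.

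**Design.** One cohort of 12 to 15 subjects, all on belumosudil (Protocol 3.1, 4.3 and 9.7.2).

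**The concern.** Two separate features of the QTcF summary need attention.

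First, the largest of many noisy readings lies above their mean even when nothing has changed. A control arm would show how large that excess is, but this trial has none. A reader who sees a mean maximum rise of, say, 17 ms cannot tell from that figure whether it reflects the drug or repeated measurement. The excess also grows with the number of ECGs, so it depends on how long each subject stays in the study.

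Second, every change for a subject is measured from the same baseline value. A Day 1 reading that happens to be low raises all of that subject's later changes together. Two pre-dose ECGs are scheduled, but the change is referred to only one of them.

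What is at stake is the reading of the maximum-change summary and of the bands above 30 and 60 ms. Protocol 9.7.1 says the trial's main purpose is to guide later studies, and its QT figures will be part of that guidance.

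**Working it through.** The plan states no QTcF variability and no expected change, so it has no figure to reproduce.

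**Inputs**
- Scheduled on-treatment ECG visits: 14 (Weeks 2 to 52). With the follow-up visit: 15 (Appendix A).
- Within-subject SD of one QTcF reading, s: not in the documents. Assumed range 5 to 15 ms.
- No drug effect, normal errors.

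**1. Expected maximum across visits.** For k independent readings minus one baseline reading, E(max change) = s × e(k), where e(k) is the expected largest of k standard normal values, e(k) = ∫ x·k·φ(x)·Φ(x)^(k−1) dx. The baseline error has mean zero and drops out. Numerical integration gives e(14) = 1.703 and e(15) = 1.736.

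| s (ms) | k = 14 | k = 15 |
|---|---|---|
| 5 | 8.5 | 8.7 |
| 8 | 13.6 | 13.9 |
| 10 | 17.0 | 17.4 |
| 12 | 20.4 | 20.8 |
| 15 | 25.6 | 26.0 |

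**2. Departures from independent single readings**, for s = 8 to 12 ms:
- First-order autocorrelation between visits (k = 15): 12.7 to 19.0 ms at 0.5, and 10.1 to 15.1 ms at 0.8.
- Triplicate means (k = 15): the SD becomes s·√(f + (1−f)/3), where f is the between-visit share of the variance. The maximum is 8.0 to 13.9 ms at s = 8 and 12.0 to 20.8 ms at s = 12 as f runs from 0 to 1.
- A subject who leaves after seven ECGs (through Week 24): e(7) = 1.352, giving 10.8 to 16.2 ms.

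The expected maximum is positive in each case.

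**3. Other readings of the SAP sentence**
- Largest of three replicates within a visit, against a mean-of-replicates baseline: e(3) = 0.846, so 0.846·s·√(1−f). This is 0 to 6.8 ms at s = 8 and 0 to 10.2 ms at s = 12.
- One ECG per visit: the within-visit maximum is simply that visit's change, with expectation zero.
- Running maximum up to each visit, at s = 10: 8.5 ms at Week 8 (k = 3), 13.5 ms at Week 24 (k = 7) and 17.0 ms at Week 52 (k = 14). This is an upward trend produced by noise alone.

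**4. Baseline averaging.** With one pre-dose ECG, the noise variance of a visit's change is s² + s² = 2s². With the mean of two it is s² + s²/2 = 1.5s², which is 25% less. Simulation (200,000 subjects, k = 15) gives:

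| s (ms) | Mean maximum: one / two baseline ECGs | Any visit >30 ms: one / two | One given visit >30 ms: one / two |
|---|---|---|---|
| 8 | 13.9 / 13.9 | 4.0% / 1.5% | 0.4% / 0.1% |
| 10 | 17.4 / 17.3 | 13.4% / 8.1% | 1.7% / 0.7% |
| 12 | 20.9 / 20.9 | 25.1% / 19.6% | 3.9% / 2.1% |

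The mean maximum does not move beyond simulation error, while the spread and the false entries fall. At s = 10 and 15 subjects, worst-visit entries above 30 ms go from 0.134 × 15 = 2.0 to 0.081 × 15 = 1.2. Worst-visit entries above 60 ms are rare either way (at s = 12, 0.26% against 0.03%).

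**5. Largest decrease as reference.** If errors are symmetric, the expected largest decrease over the same ECGs is −s × e(k), whatever s, k or the correlation. At s = 10 and k = 14, noise alone gives +17.0 and −17.0 ms. A constant 10 ms effect gives 17.0 + 10 = +27.0 and −17.0 + 10 = −7.0 ms.

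**The case against.** The strongest objection is textual. The SAP sentence says the maximum is summarised at each scheduled visit, which does not fit a single overall maximum, and the sentence before it speaks of triplicates. On a within-visit reading the excess is much smaller or zero. This stands to the extent that a maximum over all visits is one reading and not a stated rule. But the protocol schedules a plain 12-lead ECG, and with one reading per visit a within-visit maximum adds nothing to the visit-by-visit change. The word has content only across visits or across replicates, and the SAP must say which.

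A reader might infer that the screening ECG is wasted. It is not: it serves the QTcF eligibility criterion (Protocol 3.5), and under SAP 3.1.5 it is the baseline when no Day 1 value exists, which the Appendix A note allows. What holds is narrower: when both ECGs exist, only one enters the change.

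A reader might also infer that averaging the baseline removes the upward bias. Step 4 shows that it does not; the bias comes from taking a maximum.

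Finally, this is a descriptive summary in 12 to 15 subjects with no test. The subject stopping criterion in Protocol 9.6.2 uses an absolute QTc, not a change. That limits the consequence. It does not make the maximum interpretable.

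**Conclusion.** The point holds in a limited form. Taken across on-treatment visits, the maximum QTcF change has a positive expectation with no drug effect, about 1.7 times the within-subject SD. That is about 9 to 26 ms for assumed SDs of 5 to 15 ms with independent single readings, and less with correlated visits, averaged triplicates or fewer visits. The sign does not depend on the SD, but the size does, so no single figure can be attributed to the plan. Separately, using one pre-dose ECG where two exist makes the noise variance of each change one third larger than it need be (2s² against 1.5s²).

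It would go too far to say that the trial's QT findings cannot be read. Mean change by visit has zero expectation under noise alone, and the absolute QTcF bands and the by-visit listing are also planned. The difficulty is confined to the maximum and the change bands. For the bands, the larger shares in step 4 apply only if subjects are classified by their worst visit, which the SAP does not state.

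**What to change.** Amend SAP 3.9.4 in three places:

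1. Define the QTcF baseline as the mean of all available pre-dose ECGs, which is a single ECG if the Day 1 repeat is waived. Reconcile the Appendix A note with Section 5.2.1 on whether it may be waived.
2. State that the maximum is taken per subject over on-treatment visits, without the follow-up ECG, using the visit mean if triplicates are recorded. Reconcile the triplicate wording with the protocol. Say whether the change bands are by visit or by worst visit.
3. Report each subject's largest decrease beside the largest increase, over the same ECGs. Noise alone makes the two equal and opposite on average, while a sustained shift moves both the same way. The row separates noise from a shift; it cannot separate a drug effect from drift over time.

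The cost is SAP wording and one table row, with no new data. There are two downsides. The QTcF baseline would differ from the general rule in SAP 3.1.5. The screening ECG is also the eligibility ECG, so selection at 450 ms pulls the averaged baseline slightly low. In simulation, with an assumed mean QTcF of 415 or 425 ms, a between-subject SD of 20 ms and s of 8 or 12 ms, that shift was 0.2 to 1.1 ms. If the Day 1 ECG must also meet the criterion, the present rule carries almost the same shift (0.2 to 1.1 ms).
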